### 3. Research Design and Methods

This trial will be conducted in compliance with the protocol, Good Clinical Practice (GCP), and applicable regulatory requirements. Up to 50 patients with visible oral lesions fitting the clinical criteria for cancerous or precancerous lesions undergoing surgery or biopsy (as part of clinical care) at the NJMS or RSDM oral medicine clinic/Rutgers Dental Associates will be targeted for consideration as participants in this study. This includes patients with oral cancer, proliferative verrucous leukoplakia (PVL), conventional oral leukoplakia (OL), and erythroplakia, plus suspect oral papillomas and oral lichen planus. When the identified oral lesion seems appropriate, patients will be asked to sign an informed consent allowing a portion of the biopsy sample or excised tumor to be utilized for research purposes. These specimens will be transferred directly to [name] at Rowan University-SOM for preparation of cell cultures and other research-related testing.

Oral cancers will be sampled surgically by [name], [name], [name], [name] or [name]. Precancerous lesions will be biopsied surgically by [name]. This work will be performed at the NJMS/RSDM/Rutgers Dental Associates and University Hospital in Newark, NJ. Biopsy will be performed by original surgeon as determined by best care practice. These procedures will have been planned as a matter of course for the patient. Therefore, the patients’ participation in this study should not affect their treatment. The operating surgeon will place a sample of the tissue on wet ice. [name] will receive the tissue from the pathology department after they agree that this tissue is not needed for further

analysis. [name] will be waiting in a room as instructed by the surgeon and pathologist and will package the specimens on wet ice and bring them to his lab according to IATA protocols.

[name] and [name] will evaluate PDPN expression and cell morphology by IHC from formaldehyde fixed section of these samples. Surgical specimens will be fixed in 10% formalin in PBS, paraffin embedded, sectioned (4 microns), and processed for hematoxylin/eosin staining and immunohistochemistry D2-40 monoclonal antibody (Dako) to detect PDPN as described [56]. Paraffin-fixed specimens will be prepared by the local oral pathology laboratories at the University Hospital in Newark, NJ as part of the diagnostic histopathology. Routine pathology reports generated during patient care will also be examined to verify the tumor grade and nature of these specimens. Data will be examined by [name] and [name] in a blinded manner with coded labels such that they will not know whether the specimens are from MASL or placebo treated patients.

In addition to IHC analysis, [name] will establish primary cell cultures from these samples. He will evaluate cell morphology, assay PDPN expression by Western blotting, and evaluate the effects of MASL on the growth and migration of these cells by standard growth and motility assays [57]. This work will be performed at the Science Center in Stratford, NJ. Results from these studies will be used to elucidate understand how OSCC cells respond to MASL. However, these cell culture data will not be used as eligibility criteria since these assays may not be accomplished in a time frame consistent with treatment plans. The IHC analysis can be completed within 4 days. Therefore, this testing will not delay any subsequent treatment plans or options.

Patients with OSCC cells that express robust levels of PDPN will be considered for treatment. Robust levels of PDPN will be defined as greater than normal cells and equivalent or greater than PDPN levels expressed by lymphatic endothelial cells (LECs) from the same sample specimen. Patients that meet the eligibility criteria will be enrolled in the treatment phase of this study. Study clinicians ([name], [name], [name], [name], [name] or [name]) will administer MASL or placebo to enrolled subject. Patients will be given a lozenge (troche)with or without MASL added to achieve a final dosage of 100 mg per adult. Clinicians administering the lozenge and [name] are not blinded to the type of the lozenge; however, this information is not available to the pathologist who evaluates tumor pathology, cell morphology, and PDPN expression in the patient samples.

In addition to the process described above, patients already diagnosed with oral cancer/precancer who present to one of the study clinicians for definitive care may also be enrolled in the study if they consent to participation. In these situations, it is routine to request H&E-stained slides from the original surgical pathology department for review as part of the surgical planning for clinical care. For patients who consent, the study clinician or PI would also request 1-3 unstained specimens for D2-40 staining to determine PDPN expression for research purposes. Patients with OSCC cells that express robust levels of PDPN and meet the eligibility criteria will be considered for treatment phase. The remainder of the protocol remains the same.

MASL and placebo lozenges will be prepared by an approved GMP certified facility by chromatography methods established by [name] as described [57]. Lozenges will be stored at the University Hospital Pharmacy and be hand delivered to the administering doctor by study investigators listed on page 1 in a sealed plastic container labeled with the patients name and ID. This work will be performed at the NJMS/RSDM/Rutgers Dental associates and University Hospital in Newark, NJ. [name], [name], [name], [name], [name] or [name] along with [name] and [name] will perform a general physical evaluation of their respective patients before and after MASL or placebo administration. [name] or [name] will

evaluate patient vital signs including temperature, pulse, blood pressure, and overall health after administration. [name] or [name] will also assist with management of any complication should it arise.

In this approach, MASL will find administration through topical exposure to oral lesions in the mouth as the lozenge dissolves. Patients will be asked to dissolve the lozenge in their mouth for at least 5 minutes before being chewed, and refrain from spitting, eating, or drinking for at least 20 minutes after lozenge administration. Subjects will be asked to finish chewing the lozenge within 20 minutes. Systemic exposure through the blood stream may also be accomplished. Data from university studies on cell lines and animal models indicate that MASL can be applied topically or eaten to target PDPN in order to inhibit tumor cell growth and migration. However, pharmacokinetics of this compound have not been established.

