Our tertiary endpoint will be measured from the same patient resection or second biopsy material used to measure our secondary endpoint. We will compare the morphology of cells included in the oral lesion to normal oral squamous epithelial cells. Our tertiary endpoint will be met if MASL treated OSCC cells appear less dysplastic than they appeared before treatment. Dysplasia will be graded on a scale of 1 to 5, with 5 being the most dysplastic. Our hypothesis predicts that MASL treated OSCC cells will appear more cuboidal and flatter than they were before treatment.

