## Schedule of Events

Subject Recruitment	
Identification of patients with premalignant or malignant lesions during the course of clinical care (this includes previously diagnosed oral cancer/precancer patients presenting for surgical resection as part of clinical care)	[name] [name] [name] [name]
informed consent	[name] [name]
Clinical procedures as per best care practice	
Diagnostic tissue biopsy	[name] [name] [name] [name] [name] [name]
Laboratory Procedures	
Diagnostic histopathology, Evaluation of cell morphology & PDPN expression	[name] [name]
Identification of patient samples with robust PDPN expression	
Clinical procedures as per best care practice	
Planning resection or second biopsy	[name] [name] [name] [name] [name] [name]
Treatment Phase	
Evaluation of eligibility criteria for enrolment. Eligible patients: 
 
• Have tissue samples with robust PDPN expression
 
• Have not used topical steroid products within the last 2 weeks
 
• Have Eastern Cooperative Oncology Group performance status of 0 or 1.
 
• Display normal organ function as evidenced by standard laboratory blood tests including liver enzymes and creatine.
 
• Do not present evidence of comorbidities including ongoing or active infection, unstable illness, or medical conditions.
 
• Not pregnant as per standard blood or urine tests according to best care practice
 
• Not breast feeding
 
• Consent to Abstinence or use of adequate contraception (women of childbearing potential and men of reproductive potential)
 
	[name] [name] [name] [name] [name] [name]
MASL administration within 1 week of planned biopsy or resection	[name] [name] [name] [name] [name] [name] [name] [name]
Clinical procedures as per best care practice	
Planned resection or second biopsy	[name] [name] [name] [name] [name] [name]
Laboratory Procedures	
Diagnostic histopathology, Evaluation of cell morphology & PDPN expression	[name] [name]

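### Masking of the pathologists is stated for arm but not for time point, which leaves the before-versus-after dysplasia endpoint, judged within MASL patients only, open to a reading shift

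*Protocol*

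**What the plan says.** Protocol Section 3 describes the masking of the readers twice. Specimens are examined "in a blinded manner with coded labels such that they will not know whether the specimens are from MASL or placebo treated patients". The clinicians know the lozenge type, but "this information is not available to the pathologist who evaluates tumor pathology, cell morphology, and PDPN expression in the patient samples". Section 7.3 adds only a general statement that data are handled blind. None of these mentions whether a specimen was taken before or after treatment.

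The same section fixes when the first reading happens. "Patients with OSCC cells that express robust levels of PDPN will be considered for treatment", and "The IHC analysis can be completed within 4 days". The Schedule of Events puts the first evaluation of morphology and PDPN, followed by "Identification of patient samples with robust PDPN expression", ahead of the treatment phase. The second evaluation comes after the planned resection or second biopsy. Section 3 also says: "Routine pathology reports generated during patient care will also be examined to verify the tumor grade and nature of these specimens". It does not say by whom.

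Section 1.3 defines the tertiary endpoint: "Our tertiary endpoint will be met if MASL treated OSCC cells appear less dysplastic than they appeared before treatment". The measure is a reader's grade: "Dysplasia will be graded on a scale of 1 to 5, with 5 being the most dysplastic". The secondary endpoint has three parts. Two compare lesion cells with normal cells and with lymphatic endothelial cells (LECs) in the same post-treatment specimen. The third compares the PDPN decrease on MASL with that on placebo by t-test at p < 0.05.

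**The concern.** Masking to arm protects a comparison between arms. It does not protect a comparison of a patient's later reading with that patient's own earlier one. For that, the reader should not know which slide came first, and both slides should be read under the same conditions.

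The stated workflow makes this hard to achieve. The eligibility reading can only be a baseline reading, and the later specimen does not yet exist when it is made. No step re-reads the baseline slide beside the later one. The protocol also states the direction it expects: less PDPN and more normal morphology after MASL.

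The dysplasia grade is the most exposed outcome, because it is a matter of judgement and its success rule looks only at MASL patients. A tendency to grade later slides a little lower, from expectation or from a change in reading habits between sessions, would count as a MASL effect.

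**Working it through.** **1. What the masking covers.** The two specific statements in Section 3 concern MASL versus placebo, or the lozenge type. Section 7.3 gives no detail. Masking to time point is therefore not stated. It is not expressly excluded either.

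**2. What the timing implies.** First reading: before treatment, because it gates eligibility. Second reading: after treatment and surgery. The sessions are separate, and the first is known to be baseline.

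**3. How a shift enters each endpoint.** Let δ be the true mean fall on MASL, take no true fall on placebo, and let b be a spurious fall in the later reading, equal in both arms because readers do not know the arm.

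- Tertiary rule, MASL only: expected observed fall = δ + b. With δ = 0 this is b, so the shift remains in full.
- PDPN decrease, MASL versus placebo: (δ + b) − (0 + b) = δ. The shift cancels.
- PDPN versus normal cells and LECs: both cell types lie in one post-treatment specimen. No earlier reading enters, and staining or session drift acts on both.

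**4. Size for the dysplasia grade, per patient.** The protocol gives no reading error and no grade distribution, so these inputs are assumptions: no true change, underlying grades uniform from 2 to 4.5, reading error SD 0.4 to 0.6 grade, and readings rounded to whole grades 1 to 5. By simulation:

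| Assumed shift in later reading | Read lower | Read higher |
|---|---|---|
| 0 | 22–29% | 22–29% |
| 0.25 grade | 34–39% | 12–20% |
| 0.5 grade | 49–50% | 6–13% |

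The planned number on MASL is up to 10 (Section 3.3). With 10 patients, the mean grade falls in 41–43% of such no-effect trials at zero shift, 75–82% at 0.25 grade and 94–98% at 0.5 grade.

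**5. Within-arm and between-arm results compared.** Changes are normal, with no drug effect, 10 per arm, and b in SDs of the change score (assumed). The chance that the MASL mean merely looks better is Φ(b√10); for b = 0.5 this is Φ(1.58) = 94%. The within-arm t-test is only illustrative, because Section 1.3 names no test for dysplasia.

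| b (SD) | MASL mean looks better | Within-MASL t-test, p < 0.05 in favour | Between-arm t-test, p < 0.05 |
|---|---|---|---|
| 0 | 50% | 2.5% | 4.9% |
| 0.25 | 79% | 10.6% | 5.0% |
| 0.5 | 94% | 29% | 5.0% |
| 0.75 | 99% | 56% | 5.0% |
| 1 | 99.9% | 80% | 5.0% |

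A shift common to both arms inflates the within-MASL result and leaves the between-arm test at its nominal level.

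**6. Slide count for a joint re-reading.** 20 patients × 2 specimens = 40 H&E slides at one slide per specimen. Adding one D2-40 slide per specimen gives 80.

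**The case against.** A reader might infer that the pathologists are known to be unmasked to time point. The documents do not say so. Labels are coded, Section 3.6 refers to a coded sample number for research use, and Section 7.3 claims blind collection and analysis. Up to 50 patients are to be considered, so baseline and post-treatment specimens could reach the reader mixed together, and a later coded specimen need not be recognised as such. Reader names are removed, so whether the same people read both specimens cannot be checked. This stands as a limit on certainty: the point is that time-point masking is unstated and that the timing works against it. It does not remove the point, since the eligibility reading is baseline by construction and no paired re-reading is provided for.

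A reader might also infer that the secondary PDPN endpoint is biased in the same way. The documents do not support that. Its change component is tested against placebo by arm-masked readers, and its other two criteria are internal to one specimen. Separate staining and reading sessions may add noise, which has not been quantified here.

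It is also fair to object that every shift above is assumed. The tables show what a shift would do, not that one will occur. Even at zero shift, 22–29% of unchanged patients read lower, so part of the weakness lies in a rule with no placebo comparison. The fix therefore addresses both the reading and the rule.

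**Conclusion.** The concern holds in a limited form. The protocol states masking to arm and does not state masking to time point, while its own sequence separates the two readings and identifies the first as baseline. The consequence is mainly for the tertiary dysplasia endpoint, where a reading shift alone could satisfy the rule. If the shift were 0.25 to 0.5 grade, the MASL mean grade would fall in about 75–98% of trials with no true effect, against 41–43% with no shift. These figures rest on the assumed grade spread, reading error and shift; the true shift is unknown.

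For PDPN the randomised contrast is protected, provided that arm masking holds and any shift is equal in the two arms. Only possible loss of precision remains. The change is worth making because it is cheap, but it concerns a tertiary endpoint and does not threaten the MASL-versus-placebo PDPN comparison.

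**What to change.** In Section 3, state that the rapid baseline reading serves eligibility only. For the tertiary endpoint, have the same pathologists re-read each patient's pre- and post-treatment H&E slides together at the end of the study, under new codes and in random order, masked to both arm and time point. In Section 1.3, judge the tertiary endpoint on the MASL-versus-placebo difference in change of dysplasia grade, so that any remaining common shift cancels. State also that the routine pathology reports are not open to the endpoint readers before this re-reading is complete.

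Optionally, re-read the D2-40 slides in the same way. Staining both time points in one run is possible only where a spare baseline section has been kept, so retention of such sections should be settled now.

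The cost is one extra batch of about 40 H&E slides (about 80 with D2-40) plus relabelling, with no new reader, visit or biopsy. Two limits remain: masking to time point may be incomplete where the second specimen is visibly a resection, and the readers will have seen the baseline slides before.

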### 1.1 Objectives

Oral cancers will be biopsied by [name], [name], [name] and [name] and [name]. Precancerous oral lesions will be biopsied by [name]. For oral cancer/precancer patients biopsied at an outside institution and referred to Rutgers/University Hospital for care, outside H&E slides and unstained specimens for PDPN staining will be requested. [name] and [name] will evaluate tumor pathology, cell morphology, and PDPN expression in these patient samples. [name] will evaluate PDPN expression and MASL sensitivity from primary cultures of these cells. Study clinicians will evaluate oral cavity and health of their respective patients before and after MASL treatment. [name], [name], [name], [name], [name] or [name] will administer MASL dosage, evaluate any effects on oral structure and epithelium, and perform clinically indicated resection or biopsy to obtain specimen after treatment. [name], [name], [name], [name], [name] or [name] along with [name] and [name] will measure overall health before and after administration, and evaluate potential allergic reaction to MASL and respond to any unlikely scenarios. [name], [name] and [name] will evaluate pathology, cell morphology, and PDPN expression in these samples. We will determine if MASL treatment can decrease PDPN expression and normalize cell morphology in oral cancers and precancerous lesions.

Thus, primary, secondary, and tertiary objectives are as follows:

- a. Primary Objective: To evaluate and compare the morphology and podoplanin (PDPN) expression of cells included in the oral lesion initial biopsy to normal oral squamous epithelial cells (OSCCs).
- b. Secondary Objective: To evaluate and compare the PDPN expression of cells included in the resected oral lesion to normal oral squamous epithelial cells.
- c. Tertiary Objective: To evaluate and compare the morphology of cells included in the resected oral lesion to normal oral squamous epithelial cells.

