#### **6. Data and Safety Monitoring**

The effects of MASL on overall patient health and oral health will be monitored by trained physicians and dentists before and after each dose. No other drugs or devices will be given to patients. Attending investigators will evaluate adverse effects in real time. Data will be collected and stored with security measures used to protect it from loss or inappropriate use by password protection, restricted access, and, database backup.

An independent safety monitoring group has been set up for this study. The name of the Data Safety Monitoring Board (DSMB) is "MASL data safety monitoring board". The group will meet bimonthly, and will generate a written report from each meeting. These meetings will be closed to the public, and the group will be supplied with records and descriptions of patient responses in the study and scientific data that is obtained from the study. These descriptions will be complete, but the study coordinator will remove patient names and any personal identifiers before they are given to the group for evaluation. The group will use these descriptions to generate reports that

will contain 3 sections divided into: (1) Assessment of progress, (2) Presentation and analysis of any problems that arise, and (3) Recommendations based on assessment of progress and problems. Examples of problems that arise may include reactions of patients to the study drug including rashes, changes in heart rate, temperature, or breathing. Written reports will be available to the IRB since the director of the DSMB will send them directly to the study coordinator who will upload them to the Study Profile on the eIRB website. The group will be made up of the following professionals which include basic scientists (PhD) and a physician (MD, PhD) with experience in molecular and cell biology, acute reactions and shock, nutrition and digestion, and biostatistics:

Name and degrees	Position	Affiliation	Expertise
[name]	Assistant [name] and cell biology, physiology, acute reactions and shock ([name] will serve as DSMB director)
[name].	[name] transduction, tumor cell survival and migration, chemotherapy mechanisms
[name].	[name] and clinical research analysis and biostatistics
[name].	[name], digestion, effect of compounds on disease including diabetes, Alzheimer's, and autism, and research ombudsman

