### 7.3 Professional Reporting

Data will be collected and analyzed in a blind manner. Results will be published in peer reviewed journals to share results of this research with the scientific community.

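### Section 7.3 says data are collected blind, but Section 3 masks only the pathology reading, so clinical and safety assessments, and to a lesser degree the post-treatment specimen, are open to arm-aware bias

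*Protocol*

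**What the plan says.** **Who is masked.** Section 3 has the slides read under coded labels by readers who do not know the arm. It then says that the clinicians who give the lozenge, and one further named person, "are not blinded to the type of the lozenge; however, this information is not available to the pathologist".

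**What the unmasked clinicians do.** Section 1.1 assigns three tasks to one list of clinicians in one sentence: they "will administer MASL dosage, evaluate any effects on oral structure and epithelium, and perform clinically indicated resection or biopsy to obtain specimen after treatment". A list of the same length, with two others, "will measure overall health before and after administration, and evaluate potential allergic reaction to MASL". Section 6 adds: "Attending investigators will evaluate adverse effects in real time". No masked assessor is named for any of this.

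**What is claimed overall.** Section 7.3: "Data will be collected and analyzed in a blind manner".

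**What is already in place.** Section 3 describes a placebo lozenge from the same facility as MASL, storage at the University Hospital Pharmacy, and hand delivery "in a sealed plastic container labeled with the patients name and ID". The Schedule of Events has "MASL administration within 1 week of planned biopsy or resection", listed after the planning of that procedure.

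**The concern.** A placebo lozenge is there so that the two arms are handled and judged alike. Here the people who handle and judge the patients know the arm, and the protocol gives no reason for it. Two things are at stake.

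- **Clinical and safety assessments.** Effects on the mouth, general health and possible reactions are judged at the chairside and never reach a coded slide. Sections 2 and 4.1.1 both say that no human safety studies of MASL have been reported, so the placebo arm is the only internal yardstick for separating drug reactions from background. The monitoring board in Section 6 works from supplied records and descriptions of patient responses, and the assessments behind those are made by clinicians who know the arm.
- **The post-treatment specimen.** The secondary endpoint in Section 1.3 needs a larger PDPN decrease after MASL than after placebo, tested by t-test. The tertiary dysplasia grade uses the same tissue. A masked reader can score only the tissue that was taken, and the protocol gives no sampling-site rule beyond best care practice.

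Separately, if Section 7.3 is carried into a publication as it stands, it will describe the trial wrongly.

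**Working it through.** The point rests on the text, and the plan states no figure to reproduce. I first set the sections side by side, then size the specimen route under stated assumptions.

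**1. Text comparison**

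| Step | Done by | Masked? |
|---|---|---|
| Initial biopsy (primary endpoint; 1.1, 1.3) | Surgeons, before any lozenge | Not at issue: no treatment yet |
| Giving the lozenge (3) | Study clinicians | No, stated |
| Evaluating oral effects (1.1) | Same list as dosing | No, follows from Section 3 |
| Taking the post-treatment specimen (1.1) | Same list as dosing | No, follows from Section 3 |
| Overall health and allergic reaction (1.1) | List of the same length, with two others | No masked person named |
| Vital signs after dosing (3) | One of two people | Not stated |
| Adverse effects (6) | Attending investigators | No masked person named |
| Slide reading (3) | Pathology readers, coded labels | Yes, stated |

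Section 7.3 claims blinding for collection as well as analysis. The table supports that for slide reading only, and no other section repairs the conflict.

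**2. Illustration of the specimen route**

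Inputs from the protocol: 10 per arm (Section 3.3); a t-test at 0.05 on the degree of PDPN decrease (Section 1.3). The test's sidedness is not stated, so I take it as two-sided.

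Assumptions not in the protocol: no true effect; two candidate sites per lesion, normally distributed with within-lesion SD w; in the MASL arm the clinician takes the site guessed to have lower PDPN, the guess correlating r with true PDPN; in the placebo arm the site is random.

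- The expected value of the lower of two independent standard normals is −1/√π = −0.564. An imperfect guess shifts the post-treatment value by 0.564 × r × w.
- In the decrease from baseline, the between-lesion level cancels. Its SD is about √2 × w, because one baseline site and one post-treatment site each contribute w².
- Standardised shift: δ = 0.564r/√2 = 0.399r.
- Noncentrality: δ × √(n/2) = δ × √5, with 18 degrees of freedom and critical value 2.101.

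| r | δ | Noncentrality | Rejections favouring MASL |
|---|---|---|---|
| 0 | 0 | 0 | 2.5% |
| 0.25 | 0.100 | 0.223 | 4.0% |
| 0.5 | 0.199 | 0.446 | 6.2% |

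Simulating the same model (200,000 trials per setting) gives about 4.0% and 6.2% to 6.3%. The results do not depend on how total variance splits between and within lesions, because the change score removes the between-lesion part.

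No comparable figure can be given for the clinical and safety assessments: the protocol supplies no event rates or scoring from which to compute one.

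**The case against.** The best defence is that the efficacy measurement is already protected where it matters most, and much of it stands.

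- **The slide reading is masked and coded.** True, and this protects the scoring. It does not reach the choice of tissue or any bedside assessment.
- **The procedure is planned beforehand.** Section 3 and inclusion item 6 make it part of routine care, and the Schedule of Events places its planning before the treatment phase. Paraffin specimens are prepared by the hospital's pathology laboratories. This leaves little room for choice with a resection and more with a second biopsy. It narrows the specimen route without closing it.
- **PDPN is read by immunohistochemistry.** Nothing says that it can be seen at surgery. A reader might infer very large error rates by supposing that the surgeon always picks the lower site; in the model above that gives about 14%, and higher still if the opposite choice is made under placebo. The documents do not support such selection, so only imperfect guesses are used here.
- **Safety.** No between-arm safety test is defined, an independent board reviews responses, and open dosing may be understandable with no prior human safety study. The protocol does not state that reason, however, and the reaction management in Section 4.3 is driven by signs and symptoms, not by arm.

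Two further inferences should be resisted. A reader might think the main result is compromised: the primary endpoint uses the initial biopsy, so it is not. A reader might also think that recruiters know the next allocation. Names are removed, so overlap between recruiters and dosing clinicians is inferred only from matching counts and from patients entering through study clinicians. Nothing says the arm is known at recruitment.

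**Conclusion.** The concern holds within limits. Sections 3 and 7.3 contradict each other about blind data collection; this needs no assumption. Assessment of clinical effects and safety by clinicians who know the arm is an avoidable weakness. The specimen for the secondary and tertiary endpoints is exposed to a lesser degree, mainly where it is a second biopsy. The primary endpoint is not affected.

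For the specimen route, the illustrative rise in false positives favouring MASL is from 2.5% to about 4% to 6%. That range depends wholly on the assumed site-guess correlation of 0.25 to 0.5, two candidate sites, selection in the MASL arm only, and a two-sided test. It shows the order of size and does not predict what these clinicians would do. The matter should be corrected; it does not invalidate the design.

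**What to change.** 1. Have the University Hospital Pharmacy hold the allocation list and dispense MASL and placebo lozenges in coded sealed containers, with a code-break procedure kept there.
2. Keep the dosing clinicians, and the further person now named as unblinded, masked until the specimens are scored and the data are locked.
3. Reconcile Sections 3 and 7.3 in either case. If the lozenges cannot be made indistinguishable, reword 7.3 so that blinding is claimed for the pathology reading only, and report the clinical and safety assessments as unblinded.

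Cost: coded labels, a code-break procedure and protocol wording, with no extra patients or readers, since the placebo, the pharmacy and the sealed containers already exist. The uncertain item is the lozenge itself. The protocol does not say that the two match in appearance or taste, so this must be checked first. If they differ, full masking could require reformulation at the manufacturing facility, and the rewording in step 3 becomes the practical minimum.
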